5.6 Rescue Medications & Supportive Care

5.6.1 Supportive Care Guidelines

Subjects should receive appropriate supportive care measures as deemed necessary by the treating investigator. Suggested supportive care measures for the management of AEs with potential immunologic etiology are outlined along with the dose modification guidelines in Section 5.2.1.2, [Table 3](#). Where appropriate, these guidelines include the use of oral or IV treatment with corticosteroids, as well as additional anti-inflammatory agents if symptoms do not improve with administration of corticosteroids. Note that several courses of steroid tapering may be necessary as symptoms may worsen when the steroid dose is decreased. For each disorder, attempts should be made to rule out other causes such as metastatic disease or bacterial or viral infection, which might require additional supportive care. The treatment guidelines are intended to be applied when the Investigator determines the events to be related to pembrolizumab.

Note: If after the evaluation of the event, it is determined not to be related to pembrolizumab, the Investigator does not need to follow the treatment guidance. Refer to [Table 3](#) in Section 5.2.1.2 for guidelines regarding dose modification and supportive care.

It may be necessary to perform conditional procedures such as bronchoscopy, endoscopy, or skin photography as part of evaluation of the event.

5.6.2 Radiotherapy

The use of radiotherapy or surgical intervention while on study must be recorded in the trial database.

Localized palliative radiation therapy to a site of pre-existing disease may be permitted while on study. However, if the subject develops a new lesion or a definite increase in the size of existing bone or visceral lesions with or without extension into the soft tissue that meets the criteria for disease progression according to PCWG3, treatment must be discontinued for PD regardless of whether radiation therapy is initiated.

5.7 Diet/Activity/Other Considerations

5.7.1 Diet

Subjects should maintain a normal diet unless modifications are required to manage an AE such as diarrhea, nausea, or vomiting.

5.8 Subject Withdrawal/Discontinuation Criteria

5.8.1 Discontinuation of Treatment

Discontinuation of treatment does not represent withdrawal from the trial.

As certain data on clinical events beyond treatment discontinuation may be important to the study, they must be collected through the subject's last scheduled follow-up, even if the subject has discontinued treatment. Therefore, all subjects who discontinue trial treatment prior to completion of the treatment will still continue to participate in the trial as specified in Section 6.0 - Trial Flow Chart and Section 7.1.5.3 – Post Treatment.

Subjects may discontinue treatment at any time for any reason or be dropped from treatment at the discretion of the investigator should any untoward effect occur. In addition, a subject may be discontinued from treatment by the investigator or the Sponsor if treatment is inappropriate, the trial plan is violated, or for administrative and/or other safety reasons. Specific details regarding procedures to be performed at treatment discontinuation are provided in Section 7.1.4 – Other Procedures.

A subject must be discontinued from treatment but continue to be monitored in the trial for any of the following reasons:

- The subject or subject's legally acceptable representative requests to discontinue treatment.
- The subject has a medical condition or personal circumstance which, in the opinion of the investigator and/or sponsor, placed the subject at unnecessary risk from continued administration of study drug.
- The subject has a positive urine drug screen at any time during the course of the trial.
- Documented disease progression as assessed by the investigator using PCWG3-modified RECIST 1.1 guidelines (Section 7.1.2.6.1 – Initial Tumor Imaging). Two consecutive assessments are needed for disease progression. Clinical deterioration will not be considered progression.
- Unacceptable adverse experiences as described in Section 5.2.1.2 – Dose Modification (Escalation/Titration/Other) and Section 5.6.1 – Supportive Care Guidelines
- Intercurrent illness that prevents further administration of treatment
- Noncompliance with trial treatment or procedure requirements
- Administrative reasons

Cohorts 4 and 5: If subjects have to discontinue enzalutamide treatment after being enrolled into the study due to adverse events or toxicity attributed to enzalutamide, subjects can continue to receive pembrolizumab as long as they experience clinical benefit without signs of disease progression and tolerable safety.

For subjects who are discontinued from treatment but continue to be monitored in the trial, all visits and procedures, as outlined in the trial flowchart, should be completed.

Subjects may be allowed to begin treatment again if deemed medically appropriate.

5.8.2 Withdrawal from the Trial

Subjects may withdraw from the trial at any time for any reason. If a subject withdraws from the trial, they will no longer receive treatment or be followed at scheduled protocol visits.

A subject must be withdrawn from the trial if:

- The subject or subject's legally acceptable representative withdraws consent from the trial.
- The subject is lost to follow-up.

Specific details regarding procedures to be performed at the time of withdrawal from the trial including specific details regarding withdrawal from Future Biomedical Research are outlined in Section 7.1.4 – Other Procedures.

5.9 Subject Replacement Strategy

A subject who discontinues from the trial will not be replaced.

5.10 Beginning and End of the Trial

The overall trial begins when the first subject signs the informed consent form. The overall trial ends when the last subject completes the last study-related phone-call or visit, discontinues from the trial or is lost to follow-up (i.e. the subject is unable to be contacted by the investigator).

Upon study completion, participants are discontinued and may be enrolled in a pembrolizumab extension study, if available.

5.11 Clinical Criteria for Early Trial Termination

Early trial termination will be the result of the criteria specified below:

1. Quality or quantity of data recording is inaccurate or incomplete,
2. Poor adherence to protocol and regulatory requirements,
3. Plans to modify or discontinue the development of the study drug pembrolizumab.

In the event of Sponsor decision to no longer supply study drug pembrolizumab, ample notification will be provided so that appropriate adjustments to subject treatment can be made.

6.0 TRIAL FLOW CHART

6.1 Study Flow Chart

Trial Period:	Screening Phase	Treatment Cycles ^b								End of Treatment	Post-Treatment		
		1	2	3	4	To be repeated beyond 8 cycles					DC	Safety Follow-up ^c	Follow Up Visits ^d
Treatment Cycle/Title:	Screening (Visit 1) ^a					5	6	7	8	DC	30 days after last dose (±3 days)	Every 9 or 12 weeks (±7 days)	Every 12 weeks (±7 days)
Scheduling Window (Days):	-42 to -1		±3	±3	±3	±3	±3	±3	±3	At time of DC			
Administrative Procedures													
Informed Consent	X ^f												
Informed Consent for FBR (optional)	X												
Inclusion/Exclusion Criteria	X												
Subject Identification Card	X (dispense)									X (collect)			
Demographics and Medical History	X												
Prior and Concomitant Medication Review	X ^g	X	X	X	X	X	X	X	X	X	X ^g		
Trial Treatment Administration		X ^h	X	X	X	X	X	X	X				
Subsequent Anticancer Therapy Status												X	X
Survival Status ⁱ		←-----→									←-----→		X
Clinical Procedures/Assessments													
AE/SAE Monitoring	X	X	X	X	X	X	X	X	X	X	X ^j	X ^j	
Full Physical Examination ^k	X									X			
Directed Physical Examination ^k		X	X	X	X	X	X	X	X				
Vital Signs and Weight ^l	X	X	X	X	X	X	X	X	X	X			
12-Lead ECG	X												
ECOG Performance Status	X	X	X	X	X	X	X	X	X ^m	X			
Laboratory Procedures/Assessments: analysis performed by LOCAL laboratory													
PT/INR and PTT/aPTT	X ⁿ												
CBC with Differential ^o	X ⁿ		X	X	X	X	X	X	X	X	X ^p		
Comprehensive Chemistry Panel ^o	X ⁿ		X	X	X	X	X	X	X	X	X ^p		
Urinalysis ^{o,q}	X ⁿ		X ^q		X		X		X	X	X ^p		
T3, FT4 and TSH ^o	X ⁿ		X ^q		X		X		X	X	X ^p		

Trial Period:	Screening Phase	Treatment Cycles ^b								End of Treatment	Post-Treatment		
		1	2	3	4	To be repeated beyond 8 cycles					DC	Safety Follow-up ^c	Follow Up Visits ^d
Treatment Cycle/Title:	Screening (Visit 1) ^a					5	6	7	8				
Scheduling Window (Days):	-42 to -1		±3	±3	±3	±3	±3	±3	±3	At time of DC	30 days after last dose (±3 days)	Every 9 or 12 weeks (±7 days)	Every 12 weeks (±7 days)
Total Testosterone ^o	X ⁿ				X ^r				X	X			
Laboratory Procedures/Assessments: analysis performed by CENTRAL laboratory													
Tumor Marker Assessment (PSA) ^s	X				X			X		X		X	
PSA for Cohorts 4 and 5 ^s	X		X	X	X			X		X		X	
Anti-drug Antibodies (ADA) ^t		X	X		X			X		X			
Pembrolizumab Pharmacokinetics (serum) ^t		X ^u	X		X			X		X			
Blood for CTC		X ^{v, w}								X			
Blood for AR-V7 ^v		X											
Efficacy Measurements													
Tumor Imaging ^s (CT/MRI/bone scan)	X ^x				X			X		X ^y		X ^z	
Tumor Tissue Collection/Correlative and Biomarker Studies													
Tumor Tissue Collection (Newly Obtained and Archival)	X ^{aa}												
Blood for Genetic Analyses		X ^{bb}											
Blood RNA Analyses ^{cc}		X	X			X				X			
Blood for Plasma Biomarker Analyses ^{cc}		X	X			X				X			
Blood for Serum Biomarker Analyses ^{cc}		X	X			X				X			
Blood for ctDNA (plasma) ^{dd}		X			X			X		X			
Patient Reported Outcomes													
EuroQol EQ-5D ^{ee}		X	X	X	X			X		X	X		
FACT-P ^{ee}		X	X	X	X			X		X	X		

Trial Period:	Screening Phase	Treatment Cycles ^b								End of Treatment	Post-Treatment		
		1	2	3	4	To be repeated beyond 8 cycles					DC	Safety Follow-up ^c	Follow Up Visits ^d
Treatment Cycle/Title:	Screening (Visit 1) ^a					5	6	7	8	At time of DC			
Scheduling Window (Days):	-42 to -1		±3	±3	±3	±3	±3	±3	±3				

Abbreviations: AE = adverse event; aPTT = activated partial thromboplastin time; AR-V7 = androgen receptor variant 7; CBC = complete blood count; CT = computed tomography; CTC = circulating tumor cells; ctDNA = circulating tumor cell DNA; DC = discontinuation; ECG = electrocardiogram; ECOG = Eastern Cooperative Oncology Group; FACT-P = functional assessment of cancer therapy-prostate; FBR = future biomedical research; FT4 = free thyroxine; INR = international normalized ratio; MRI = magnetic resonance imaging; PSA = prostate-specific antigen; PT = prothrombin time; PTT = partial thromboplastin time; SAE = serious adverse event; T3 = triiodothyronine; TSH = thyroid stimulating hormone.

- a. Subjects may only be rescreened once.
- b. All treatment cycles are 3 weeks ± 3 days.
- c. If a subject initiates a new anti-cancer therapy within 30 days after the last dose of trial treatment, the 30-day Safety Follow-up visit must occur before the start of the new therapy. Once new anti-cancer therapy has been initiated the subject will move into survival follow-up.
- d. Follow-up visits must occur using the same imaging schedule the subject was on during treatment (eg, every 9 weeks [63 days ±7 days] from the date of allocation or every 12 weeks [84 days ±7 days] from the date of allocation). In subjects who discontinue study therapy without documented disease progression, every effort should be made to continue monitoring their disease status by radiologic imaging (CT/MRI and bone scans) and PSA according to the schedule that the subject was on at the time of discontinuation (eg, every 9 or 12 weeks from the date of allocation) until: 1) the start of new anti-cancer treatment, 2) documented disease progression, 3) death or 4) the end of the study, whichever occurs first.
- e. Survival follow-up begins 12 weeks from the time a subject experiences confirmed disease progression or starts a new anti-cancer treatment.
- f. Written consent must be obtained prior to performing any protocol specified procedures. Results of a test performed prior to the subject signing consent are acceptable in lieu of new screening tests if they are a part of routine clinical management and performed within the specified timeframe.
- g. Prior medications: record all medications taken within 28 days prior to the first dose of trial treatment. Concomitant medications: enter new medications started during the trial and up to 30 days after last dose of trial treatment regardless of when the safety follow-up visit occurs. All medications related to reportable SAEs and events of clinical interest (ECIs) should be recorded as defined in Section 7.2.
- h. Trial treatment should begin on the day of treatment allocation or as close as possible to the date on which the subject is allocated, ie, ≤7 days.
- i. After documented local site assessed disease progression, or the start of new anticancer treatment; contacts are approximately every 12 weeks by telephone. Updated survival status may be requested by the Sponsor at any time during the course of the study. Upon Sponsor notification, all participants who do not/will not have a scheduled study visit or study contact during the Sponsor defined time period will be contacted for their survival status (excluding participants that have a death event previously recorded).
- j. Record all AEs (including ECIs) occurring up to 30 days after the last dose of trial treatment. SAEs must be recorded up to 90 days after the last dose of trial treatment or 30 days following cessation of treatment if the subject starts new anti-cancer treatment. Treatment related SAEs must always be reported.

Trial Period:	Screening Phase	Treatment Cycles ^b								End of Treatment	Post-Treatment			
		1	2	3	4	To be repeated beyond 8 cycles					DC	Safety Follow-up ^c	Follow Up Visits ^d	Survival Follow-Up ^e
Treatment Cycle/Title:	Screening (Visit 1) ^a					5	6	7	8					
Scheduling Window (Days):	-42 to -1		±3	±3	±3	±3	±3	±3	±3	±3	At time of DC	30 days after last dose (±3 days)	Every 9 or 12 weeks (±7 days)	Every 12 weeks (±7 days)

- k. A full physical exam will be performed at screening and at treatment discontinuation; all treatment visits will include a directed physical exam.
- l. Height will be measured at screening only.
- m. Following Cycle 8, ECOG Performance Status will be performed at every other cycle (Cycles 10, 12, 14,...) and at treatment discontinuation.
- n. Laboratory procedures at screening are to be performed within 10 days prior to the first dose of trial treatment.
- o. After Cycle 1, pre-infusion laboratory procedures may be conducted up to 72 hours pre-infusion.
- p. Unresolved abnormal lab results associated with drug-related AEs should be followed until resolution.
- q. Urinalysis and thyroid function testing are done at screening, every other cycle (Cycles 2, 4, 6,...), treatment discontinuation, and the safety follow-up visit.
- r. Total testosterone will be done at screening, every fourth cycle (Cycles 4, 8, 12,...) and at treatment discontinuation
- s. Imaging assessments (CT/MRI and bone scans) and PSA should be performed every 9 weeks (63 days ±7 days) for the first year (through week 54), every 12 weeks (84 days ±7 days) in the second year, at treatment discontinuation and during follow-up. The timing of these assessments should not be adjusted for dose delays or cycle starts. For Cohorts 4 and 5, screening PSA by central results are required prior to allocation. PSA should be performed Q3W until Cycle 4.
- t. Pre-infusion (trough) PK and anti-pembrolizumab antibody (ADA) samples will be collected within 24 hours before infusion at Cycles 1, 2, 4, 6, and 8. To be collected from subjects in Cohorts 1 to 3 only.
- u. Post-dose (peak) PK samples will be drawn within 30 minutes after the end of infusion at Cycles 1 and 8. Additional single PK samples should be drawn at the following time points after Cycle 1 dosing: 24 hours (±4 hours) [Day 2], between 72 and 168 hours [Day 4-8], and 336 hours (±48 hours) [Day 15]. To be collected from subjects in Cohorts 1 to 3 only.
- v. Blood for AR-V7 and blood for CTC can be collected up to 3 days prior to infusion at Cycle 1. Leftover samples will be kept for future biomedical research if the subject signs the FBR consent.
- w. Leftover samples may be kept for FBR if the subject signs the FBR consent.
- x. The initial tumor imaging will be performed within 28 days prior to the first dose of trial treatment. Scans performed as part of routine clinical management are acceptable for use as the screening scan if they are of diagnostic quality and performed within 28 days prior to the first dose of trial treatment.
- y. If a scan was obtained within 4 weeks prior to treatment discontinuation, then another scan at discontinuation is not mandatory. Radiological evaluation should be repeated at treatment discontinuation in subjects discontinuing without confirmed disease progression (date of discontinuation ±4 weeks).
- z. In subjects who discontinue study therapy without documented disease progression, every effort should be made to continue monitoring their disease status by radiologic imaging (CT/MRI and bone scans) and PSA according to the schedule that the subject was on during study treatment (eg, every 9 weeks [63 days ±

Trial Period:	Screening Phase	Treatment Cycles ^b								End of Treatment	Post-Treatment			
		1	2	3	4	To be repeated beyond 8 cycles					DC	Safety Follow-up ^c	Follow Up Visits ^d	Survival Follow-Up ^e
Treatment Cycle/Title:	Screening (Visit 1) ^a					5	6	7	8					
Scheduling Window (Days):	-42 to -1		±3	±3	±3	±3	±3	±3	±3	±3	At time of DC	30 days after last dose (±3 days)	Every 9 or 12 weeks (±7 days)	Every 12 weeks (±7 days)

7 days] from the date of allocation or every 12 weeks [84 days ± 7 days] from the date of allocation) until: 1) the start of new anti-cancer treatment, 2) documented disease progression, 3) death or 4) the end of the study, whichever occurs first.
 
aa. Baseline tumor tissue for biomarker analysis from an archival tissue sample and/or newly obtained core or excisional biopsy (fine needle aspirate not adequate) must be sent to the testing laboratory and analyzed for adequacy prior to enrollment. Refer to Section 7.1.2.7 for details on newly obtained biopsy and/or archival specimen requirements by cohort.
 
bb. This sample should be drawn for planned analysis of the association between genetic variants in DNA and drug response. If there is either a documented law or regulation prohibiting collection, or if the IRB/IEC does not approve the collection of the sample for these purposes, then this sample will not be collected at that site. If the sample is collected, leftover extracted DNA will be stored for FBR if the subject signs the FBR consent. If the planned genetic analysis is not approved, but FBR is approved and consent is given, this sample will be collected for the purpose of FBR.
 
cc. Blood for RNA Analyses and Blood for Serum/Plasma Biomarker Analyses should be collected pre-infusion according to time points on the flow chart. Collections end at cycle 5 and should not be repeated. Leftover samples may be kept for FBR if the subject signs the FBR consent.
 
dd. Blood for ctDNA can be collected up to 3 days prior to the Cycle 1 pre-infusion (if the collection coincides with a treatment cycle) every 9 weeks (63 days ±7 days) for the first year (through week 54), every 12 weeks (84 days ±7 days) in the second year, and at treatment discontinuation. The timing of these assessments should not be adjusted for dose delays or cycle starts. Leftover samples may be kept for Future Biomedical Research if the subject signs the FBR consent.
 
ee. Electronic patient reported outcomes (ePROs) should ideally be administered prior to all study procedures (EQ-5D first, followed by FACT-P). All ePROs are to be administered pre-infusion at Cycles 1, 2, 3, and 4 and every 3 cycles thereafter (Cycle 7, 10, 13, 16, and 19), at treatment discontinuation, and again 30 days after last dose of trial treatment. If the subject does not complete the ePROs at a scheduled time point, the MISS_MODE form must be completed to capture the reason the assessment was not performed.
														

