5.2.1.2 Dose Modification (Escalation/Titration/Other)

5.2.1.2.1 Pembrolizumab

Dose modification and toxicity management for immune-related AEs associated with pembrolizumab

AEs associated with pembrolizumab exposure may represent an immunologic etiology. These immune-related AEs (irAEs) may occur shortly after the first dose or several months after the last dose of pembrolizumab treatment and may affect more than one body system simultaneously. Therefore, early recognition and initiation of treatment is critical to reduce complications. Based on existing clinical trial data, most irAEs were reversible and could be managed with interruptions of pembrolizumab, administration of corticosteroids, and/or other supportive care. For suspected irAEs, ensure adequate evaluation to confirm etiology or exclude other causes. Additional procedures or tests such as bronchoscopy, endoscopy, or skin biopsy may be included as part of the evaluation. Based on the severity of irAEs, withhold or permanently discontinue pembrolizumab and administer corticosteroids. Dose modification and toxicity management guidelines for irAEs associated with pembrolizumab are provided in [Table 3](#).

Table 3 Dose Modification and Treatment Discontinuation Guidelines for Immune-related Adverse Events Associated with Pembrolizumab

General instructions:				

 1. Corticosteroid taper should be initiated upon AE improving to Grade 1 or less and continue to taper over at least 4 weeks. 2. For situations where pembrolizumab has been withheld, pembrolizumab can be resumed after AE has been reduced to Grade 1 or 0 and corticosteroid has been tapered. Pembrolizumab should be permanently discontinued if AE does not resolve within 12 weeks of last dose or corticosteroids cannot be reduced to ≤ 10 mg prednisone or equivalent per day within 12 weeks. 3. For severe and life-threatening irAEs, IV corticosteroid should be initiated first followed by oral steroid. Other immunosuppressive treatment should be initiated if irAEs cannot be controlled by corticosteroids. 				
irAEs	Toxicity grade or conditions (NCI CTCAE v4.0)	Action taken to pembrolizumab	irAE management with corticosteroid and/or other therapies	Monitor and follow-up

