7.1.5.3.1 Survival Follow-up

Subjects who experience confirmed disease progression or start a new anticancer therapy, will move into the Survival Follow-Up Phase and should be contacted by telephone approximately every 12 weeks to assess for survival status until death, withdrawal of consent, or the end of the trial, whichever occurs first. The Sponsor may request survival status be assessed at additional time points during the course of the study. For example, these additional time points may be requested prior to an efficacy interim analysis and/or final analysis. All subjects who are not known to have died prior to the request for these additional survival status time points will be contacted at that time.

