All adverse events that occur after the consent form is signed but before treatment allocation/randomization must be reported by the investigator if they cause the subject to be excluded from the trial, or are the result of a protocol-specified intervention, including but not limited to washout or discontinuation of usual therapy, diet, placebo treatment or a procedure. From the time of treatment allocation/randomization through 30 days following cessation of treatment, all adverse events must be reported by the investigator. Such events will be recorded at each examination on the Adverse Event case report forms/worksheets. The reporting timeframe for adverse events meeting any serious criteria is described in section 7.2.3.1. The investigator will make every attempt to follow all subjects with non-serious adverse events for outcome.

Electronic reporting procedures can be found in the Electronic Data Capture (EDC) data entry guidelines. Paper reporting procedures can be found in the Investigator Trial File Binder (or equivalent).

Adverse events will not be collected for subjects during the pre-screening period (for determination of archival tissue status) as long as that subject has not undergone any protocol-specified procedure or intervention. If the subject requires a blood draw, fresh tumor biopsy etc., the subject is first required to provide consent to the main study and AEs will be captured according to guidelines for standard AE reporting.

7.2.1 Definition of an Overdose for This Protocol and Reporting of Overdose to the Sponsor

For purposes of this trial, an overdose will be defined as any dose exceeding the prescribed dose for pembrolizumab defined as any dose greater than 1000 mg or greater. No specific information is available on the treatment of overdose of pembrolizumab. In the event of overdose, pembrolizumab should be discontinued and the subject should be observed closely for signs of toxicity. Appropriate supportive treatment should be provided if clinically indicated.

If an adverse event(s) is associated with (“results from”) the overdose of Sponsor's product or vaccine, the adverse event(s) is reported as a serious adverse event, even if no other seriousness criteria are met.

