7.2.3 Immediate Reporting of Adverse Events to the Sponsor

7.2.3.1 Serious Adverse Events

A serious adverse event is any adverse event occurring at any dose or during any use of Sponsor's product that:

- Results in death;
- Is life threatening;

- Results in persistent or significant disability/incapacity;
- Results in or prolongs an existing inpatient hospitalization;
- Is a congenital anomaly/birth defect;
- Is an other important medical event.

Note: In addition to the above criteria, adverse events meeting either of the below criteria, although not serious per ICH definition, are reportable to the Sponsor in the same timeframe as SAEs to meet certain local requirements. Therefore, these events are considered serious by the Sponsor for collection purposes.

- Is a new cancer (that is not a condition of the study);
- Is associated with an overdose.

Refer to [Table 7](#) for additional details regarding each of the above criteria.

For the time period beginning when the consent form is signed until treatment allocation/randomization, any serious adverse event, or follow up to a serious adverse event, including death due to any cause other than progression of the cancer under study (reference Section 7.2.3.3 for additional details), that occurs to any subject must be reported within 24 hours to the Sponsor if it causes the subject to be excluded from the trial, or is the result of a protocol-specified intervention, including but not limited to washout or discontinuation of usual therapy, diet, placebo treatment or a procedure.

For the time period beginning at treatment allocation/randomization through 90 days following cessation of treatment, or 30 days following cessation of treatment if the subject initiates new anticancer therapy, whichever is earlier, any serious adverse event, or follow up to a serious adverse event, including death due to any cause other than progression of the cancer under study (reference Section 7.2.3.3 for additional details), whether or not related to the Sponsor's product, must be reported within 24 hours to the Sponsor either by electronic media or paper. Electronic reporting procedures can be found in the EDC data entry guidelines. Paper reporting procedures can be found in the Investigator Trial File Binder (or equivalent).

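### SAEs are due to Day 90, but subjects who stop for confirmed progression and start no new therapy have no scheduled SAE enquiry after about Day 30, and a new-therapy start on Days 31-90 leaves the cut-off unclear

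*Protocol*

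**What the plan says.** **SAE window.** Footnote j of protocol 6.1: "SAEs must be recorded up to 90 days after the last dose of trial treatment or 30 days following cessation of treatment", the shorter limit applying when new anticancer treatment is started. Protocol 7.2.3.1 sets the window for SAEs of any attribution at "90 days following cessation of treatment, or 30 days following cessation of treatment if the subject initiates new anticancer therapy, whichever is earlier". Section 2.1 and footnote h of 6.2 carry the same two limits. Footnote j and 7.2.3.1 add that treatment-related SAEs are reportable without a time limit.

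**Non-serious events.** Protocol 7.2 closes these earlier for everyone: "through 30 days following cessation of treatment, all adverse events must be reported by the investigator".

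**Scheduled contacts after treatment.** All subjects have a safety visit 30 (±3) days after the last dose. Follow-up visits every 9 or 12 weeks come after that, but only for subjects who stopped without progression (1.0, 2.1, footnote d of 6.1). After confirmed progression or a new therapy, subjects enter survival follow-up. Footnote e: "Survival follow-up begins 12 weeks from the time a subject experiences confirmed disease progression or starts a new anti-cancer treatment". Section 7.1.5.3.1 says that they "should be contacted by telephone approximately every 12 weeks to assess for survival status until death".

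**Flow chart row.** In 6.1 the AE/SAE monitoring row is marked at discontinuation, at the safety visit and at the follow-up visits, and is blank under survival follow-up. The second-course chart in 6.2 has the same pattern and the same footnotes.

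**The concern.** Safety is the first secondary objective (3.2), and SAE incidence is a planned summary (protocol 8.6.2; sSAP 3.6.2). A site that follows the chart exactly will see a subject who stops for confirmed progression at about Day 30 and will not be prompted to ask about serious events again, although it must report them for another 60 days. A subject who stops for another reason usually has a visit in that period with AE/SAE monitoring. Whether an SAE on Days 31-90 is found, rather than merely reportable if it becomes known, then depends partly on why treatment stopped.

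The second problem is the new-therapy limit. It is tied to the end of trial treatment and not to the start of the new therapy, so a start on, say, Day 75 redefines days that have already passed. The documents do not say how an SAE from those days is treated in the safety tables.

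**Working it through.** The plan states no figure for this gap, so there is none to reproduce. The check is day arithmetic, with Day 0 as the last dose.

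**Inputs from the protocol:** SAE window 90 days (6.1 footnote j; 7.2.3.1); safety visit Day 30 ±3 (6.1); first survival call 84 ±7 days after confirmed progression (6.1 column heading and footnote e); follow-up visits every 63 or 84 days from allocation (footnote d); new-therapy limit 30 days after cessation (7.2.3.1).

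**Assumption, not in the documents:** the gap g from last dose to confirmed progression. I take 0 to 21 days if dosing continued to confirmation, and 28 to 42 days if it was held while the confirmatory scan was awaited (Table 5 asks for at least 4 weeks for soft tissue and at least 6 weeks for bone).

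1. **Days with a duty but no scheduled enquiry** = 90 − day of safety visit.
   - Visit on Day 27: 90 − 27 = 63 days (70%).
   - Visit on Day 30: 90 − 30 = 60 days (67%).
   - Visit on Day 33: 90 − 33 = 57 days (63%).
   - If dosing was held, the discontinuation visit, which has AE/SAE monitoring, may come later. On Day 42, for example, 90 − 42 = 48 days remain.

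2. **First survival call** = g + 84 ±7.
   - g = 0: Days 77 to 91.
   - g = 6: Days 83 to 97, nominal Day 90.
   - g = 21: Days 98 to 112.
   - g = 42: Days 119 to 133.
   - A nominal call falls by Day 90 only if g ≤ 90 − 84 = 6 days, and one at the earliest edge only if g ≤ 90 − 77 = 13 days. In either case no AE/SAE question is scheduled.

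3. **Comparison group.** Follow-up visits are timed from allocation. If their timing relative to the last dose is uniform (assumption), a visit falls in the 60 days after Day 30 for about 60/63 = 95% of subjects on the 9-week schedule and 60/84 = 71% on the 12-week schedule. Coverage without progression is better, but not complete.

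4. **New therapy on Day T.** Days already elapsed beyond the 30-day limit = max(0, T − 30).
   - T ≤ 30: 0 days.
   - T = 31: 1 day.
   - T = 45: 15 days.
   - T = 60: 30 days.
   - T = 75: 45 days.
   - T = 90: 60 days.
   - Example: an unrelated-rated SAE on Day 50 is inside the 90-day window when it occurs and is due within 24 hours of being known. If new therapy starts on Day 75, the wording of 7.2.3.1 puts the window end at Day 30, before that event. Neither protocol 8.6.2 nor sSAP 3.6.2 gives a safety-analysis cut-off that would settle its status.

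**The case against.** The reporting duty does not depend on a visit. SAEs are reportable to Day 90 and must be followed for outcome, and related SAEs are reportable at any time. Section 5.8.1 also says that subjects taken off treatment, for progression among other reasons, stay under monitoring and that event data are collected through the last scheduled follow-up. This stands, and it narrows the loss to active finding of new SAEs, mainly those rated unrelated. It does not close the gap: 5.8.1 refers back to the flow chart, where the survival column has no AE/SAE entry, and the open-ended rule for related SAEs works only if the event reaches the investigator.

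It is also fair that the gap concerns only living subjects with confirmed progression and no new therapy. Once new therapy starts, the present wording leaves no duty beyond Day 30. The documents give neither the share who stop for progression nor the share of those who start no new therapy by Day 90, so no count of affected subjects can be given.

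Three stronger readings are tempting, and the documents do not support them.

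- A reader might infer that capture of late immune-related events in general depends on outcome, because "These immune-related AEs (irAEs) may occur shortly after the first dose or several months after the last dose of pembrolizumab treatment" (5.2.1.2.1). Non-serious events close at Day 30 for every subject, and related serious ones are reportable at any time in both groups. That sentence belongs to toxicity guidance and sets no collection window. A longer window for non-serious immune-related events would be a trade-off, not the repair of a contradiction.
- A reader might infer that SAEs already reported are withdrawn when new therapy starts. No section says so. Their status is undefined, which is a smaller claim.
- A reader might infer that nobody who stops for progression has any safety contact after Day 30. A late discontinuation visit is possible when dosing was held, and the gap concerns scheduled contacts only.

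Last, the current text is Amendment 07, which adds trial-completion wording. If most treatment has ended, which the documents do not state, a change would reach few subjects and leave two collection rules in one database.

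**Conclusion.** The concern holds in this limited form. For subjects who stop for confirmed progression and start no new therapy, about 60 of the 90 days of required SAE collection (57 to 63 with the visit window) have no scheduled enquiry. The period is shorter if a held dose moves the discontinuation visit past Day 30. This size rests on the protocol's own windows; only the timing of the first survival call needs the assumed gap to confirmed progression. The consequence is uneven active enquiry about SAEs by reason for stopping, chiefly for those rated unrelated.

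Separately, a new-therapy start on Days 31-90 leaves between 1 and 60 elapsed days in which the status of unrelated-rated SAEs is unclear. The primary response-rate estimate is unaffected. A change is worth making because a site that follows the chart exactly would leave required SAEs unasked for.

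**What to change.** (a) In the survival column of 6.1 and 6.2, add an AE/SAE entry for one telephone contact at about Day 90 after the last dose, obtained by re-timing the first survival call, and align footnote e of 6.1, footnote d of 6.2 and section 7.1.5.3.1. The call should ask about SAEs up to Day 90, or up to the start of new therapy if that came first.

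(b) Reword the SAE window in 2.1, footnote j of 6.1, footnote h of 6.2 and 7.2.3.1 so that it ends at Day 90 or at the start of new anticancer therapy, whichever is earlier, but not before Day 30. State the same cut-off for the safety analysis in protocol 8.6.2 and sSAP 3.6.2.

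The cost is an amendment, one re-timed call with one more question, slightly more data entry and some additional background events. If the change comes when part of the data has already been collected, the report should say which subjects fell under which rule. No treatment rule changes, and the window for non-serious events stays as it is.
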